The study treatment is TH-302, administered at doses of 340 mg/m² by intravenous infusion on days 8 and 22 in combination with sunitinib given orally at 37.5 mg per day continuously from day 1 through to day 28 of a 28-day treatment cycle. Patients will receive the study treatment until radiological progression is confirmed according to RECIST criteria version 1.1, or until treatment discontinuation is considered to be in the best interests of the patient, at the discretion of the investigator (these decisions will balance maximum benefit with acceptable tolerability). Patients will continue taking the study treatment at the discretion of the investigator should they experience clinical benefit.

A phase II trial to assess the activity and safety of TH-302 in combination with sunitinib in patients

Tumour response will be assessed every 8 weeks, regardless of any delay which may arise due to toxicity. To prevent the introduction of bias associated with treatment duration, compliance with the assessment schedule is essential.

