6. TREATMENT

6.1 Treatment Administration

6.1.1. Sunitinib

Sunitinib will be provided by the Trial Sponsor. Sunitinib will be administered at a dose of 37.5 mg per day (1 capsule of 25 mg and 1 capsule of 12.5 mg) orally for 28 days on an ongoing basis. It must always be taken at the same time every day (or as close as possible) and capsules must be swallowed whole. Food does not appear to affect the bioavailability of the drug. A 37.5 mg dose was chosen based on the approved dose of sunitinib for the treatment of pancreatic neuroendocrine tumours (pNET). If the patient requires a sunitinib dose reduction, the dose adjustment stated in section 6.3 will be followed.

On days when TH-302 is also administered, sunitinib must be taken 2 hours before, or at least 2 hours after TH-302 infusion. Given its hypoxia-inducing ability in highly vascular tumour tissue and its TH-302-enhancing effect, sunitinib will be administered as monotherapy in the first week of treatment.

If, for any reason, the patient skips a dose or vomits after ingestion, a double dose should not be taken the following day. Treatment will resume on the following day with the usual daily dose. In contrast, if for any reason an additional dose is taken, the following day's dose should be skipped.

The study drug will be supplied in 25 mg and 12.5 mg capsules. The study drug must be handled and stored safely and as specified on the label. The label on the bottles will indicate the study protocol number, the medication or bottle number, the contents, instructions for use, storage instructions, the clinical trial declaration and the name of the sponsor. The patient number will be allocated to a bottle upon hand over.

Patients will be instructed as to its correct administration and that it must be kept at room temperature (15-25 °C) and out of the reach of children. Site staff must ensure that the patient understands the instructions for correct outpatient use of the drug.

Patients will receive enough medication until the next visit, and must return the containers with any surplus medication for it to be accounted for. This will take place on day 1 of each cycle prior to dispensation of medication for the next cycle. Any surplus medication returned by the patient for it to be accounted for will not be dispensed again, and the number of surplus sunitinib tablets will be recorded. If the dose is modified during a medical visit, the patient will return all surplus prior medication.

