6.3. Titration of the Study Drug

All dose modifications must be conducted according to the most severe preceding toxicity, as classified by the *National Cancer Institute Common Terminology Criteria for Adverse Events* (NCI-CTCAE, version 4.0).

As far as possible, an attempt should be made to follow the dose and scheduled regimen. However, in case of an adverse event, administration of the study drug should be titrated as described below.

The patient should notify the investigator of the date of onset of any adverse signs and symptoms.

Dose modifications to both treatments may be required in 3 different situations:

- During a cycle: treatment is discontinued until recovery and the dose is reduced, if necessary, during a particular treatment cycle.
- Between different cycles: treatment administration is delayed in the next cycle due to persistence of residual toxicity at the beginning of a new cycle.
- During the following cycle: the dose is reduced in the following cycle, taking into account the toxicity exhibited in the previous cycle.

In the event of treatment delay, proceed as follows:

- On day 1 of a cycle, if the administration of sunitinib must be postponed, the whole cycle must be delayed.

A phase II trial to assess the activity and safety of TH-302 in combination with sunitinib in patients

- On days 8 or 22, if the administration of both drugs must be postponed, that dose must be skipped.
- On days 8 or 22, if the administration of just 1 drug must be postponed, that dose will be skipped and the cycle will not be delayed, but rather the other drug will be administered on its own.

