6.3.1. Discontinuation of Treatment

The treatment will be temporarily discontinued until the resolution of \leq grade 2 toxicity. Depending on the duration of treatment discontinuation, this will either lead to the loss of all subsequent scheduled doses within the same cycle, or even delay the start of the next cycle. If the patient recovers from the adverse event within the same cycle, therapy may be continued in that cycle. Any missed doses for toxicity will not be made up for within the same cycle.

Dose reduction when reintroducing the treatment is determined below (section 6.3.3), unless, in the event of disagreement, the investigator prefers to discuss it with GETNE [contact]. If a dose is reduced within a cycle, the patient should return to the site to receive the new treatment dose.

If treatment discontinuation lasts $>$ 4 weeks, for reasons other than study treatment toxicity (non-cancer surgery, etc.), GETNE must be consulted before reintroducing the study drug

Treatment will be discontinued permanently in the following situations:

- The patient requires more than 2 dose-reduction steps.
- The patient requires more than 4 weeks delay (one full cycle) to restart treatment due to study treatment toxicity.

In patients for whom recovery from treatment toxicity involves treatment suspension lasting more than 4 weeks, or delaying a treatment cycle, but there is a clear clinical benefit in the opinion of the investigator, reintroduction of the treatment may be discussed with GETNE

Patients who discontinue treatment with TH-302 may continue receiving sunitinib as monotherapy within the trial.

Under no circumstances may patients receive TH-302 as monotherapy. In the event that the administration of sunitinib must be discontinued, the administration of TH-302 will also be discontinued.

Patients who permanently discontinue TH-302 and sunitinib will abandon active treatment and enter the follow-up phase.

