6.3.3. Dose Reduction

Titration is not required in patients with grade 1 or 2 treatment-related toxicity. Despite this, investigators should always treat their patients according to their medical judgement and based on individual circumstances.

2 dose-reduction steps are permitted depending on the type and severity of toxicity. If the investigator deems it to be necessary, the reduction of the two dose levels can be performed directly, without needing to wait for a time between both.

Patients requiring more than 2 dose reductions will abandon the treatment phase and enter the follow-up phase.

All adjustments or dose modifications should be clearly documented in the patient's medical record and in the CRF (Investigational product administration).

Once a patient's dose has been reduced, all subsequent cycles will be administered at that same dose, unless a further reduction is required. Dose reescalation will not be permitted as part of the study. Specific cases will be discussed with the study's coordinating investigator [REDACTED]

Table 1. Available dose levels with TH-302 and sunitinib

DOSE LEVEL	TH-302 DOSE	SUNITINIB DOSE
Starting	340 mg/m ² D8, 22	37.5 mg/24h D1-28
-1	280 mg/m ² D8, 22	37.5 mg/24h D1-28
-2	280 mg/m ² D8, 22	37.5 mg/24h D1-22, plus a rest week (3 weeks on / 1 week off)

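### Protocol Table 1 describes the level -2 sunitinib schedule in two ways that differ by one day, and that day (day 22) is a TH-302 infusion day

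*Protocol*

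**What the plan says.** Protocol Section 5.1 has sunitinib given "continuously from day 1 through to day 28 of a 28-day treatment cycle", with TH-302 on days 8 and 22. Table 1 in Section 6.3.3 keeps those TH-302 days at every dose level. For sunitinib, the starting level and level -1 both read "37.5 mg/24h D1-28". Level -2 reads "D1-22, plus a rest week (3 weeks on / 1 week off", with TH-302 280 mg/m² still on days 8 and 22.

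Three other rules bear on day 22:

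- Section 6.1.1, on timing: "On days when TH-302 is also administered, sunitinib must be taken 2 hours before, or at least 2 hours after TH-302 infusion".
- Section 6.3.1, on stopping one drug: "Under no circumstances may patients receive TH-302 as monotherapy", followed by "In the event that the administration of sunitinib must be discontinued, the administration of TH-302 will also be discontinued".
- Section 6.3, on postponing just one drug on day 8 or 22: that dose is skipped and "the cycle will not be delayed, but rather the other drug will be administered on its own".

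The SAP repeats the starting doses in its treatment sections but does not restate the level -2 schedule.

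**The concern.** A single table cell gives a day range and a weekly pattern that do not agree. A one-day slip would often be trivial, but here the day in question is an infusion day. A pharmacist or investigator reading the cell cannot tell whether the patient should take sunitinib on the day of the second TH-302 infusion.

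If day 22 is a rest day, the Section 6.1.1 instruction on spacing sunitinib around the infusion cannot be followed. The ban on TH-302 alone in Section 6.3.1 may also be engaged.

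The ambiguity would tend to recur in each patient it reaches. Section 6.3.3 allows both reduction steps to be taken at once, Table 3 sends some grade 4 events straight to level -2, and re-escalation is not part of the study. Ten sites have to read the cell.

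It also affects the data. A day-22 sunitinib dose that is not taken is an omission on one reading and correct dosing on the other. That feeds the 80% compliance rule in Section 6.1.1 and the omission counts in SAP Table 11.

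**Working it through.** **Inputs**

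- Cycle length: 28 days (Section 5.1).
- Counting convention: D1-28 denotes the full 28-day cycle in the same column of Table 1, so ranges include both end days.
- Level -2 sunitinib as a range: days 1 to 22, then a rest week (Table 1).
- Level -2 sunitinib as a pattern: three weeks on, one week off (same cell).
- Level -2 TH-302: days 8 and 22 (same row).
- Daily sunitinib dose at level -2: 37.5 mg.

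**Length of each schedule**

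- Range plus a full rest week: 22 + 7 = 29 days, one more than the cycle.
- Range held to the cycle: 28 - 22 = 6 rest days (days 23 to 28), which is not a week.
- Weekly pattern: 21 + 7 = 28 days, which fits the cycle but ends sunitinib on day 21.

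The plan's own equation of the two descriptions therefore cannot be reproduced. The part that fails to fit 28 days is the range with a full rest week; the weekly pattern on its own does fit.

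**Position of the TH-302 infusions**

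| Reading | Sunitinib days | Rest days in a 28-day cycle | Day 8 | Day 22 |
|---|---|---|---|---|
| Day range | 1 to 22 | 23 to 28 (6 days) | on sunitinib | on sunitinib |
| Weekly pattern | 1 to 21 | 22 to 28 (7 days) | on sunitinib | first day off |

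**Exposure per level -2 cycle**

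- Day range: 22 × 37.5 = 825 mg, and 22/28 = 78.6% of the continuous amount.
- Weekly pattern: 21 × 37.5 = 787.5 mg, and 21/28 = 75.0%.
- Difference: 37.5 mg, one daily dose.

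**Compliance**

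The protocol does not say over what period the 80% rule is applied; assume one cycle for illustration. A patient who takes 17 doses has 17/22 = 77.3% on the day range (below the threshold) and 17/21 = 81.0% on the weekly pattern (above it).

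**Tumour assessments**

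If a site ran 29-day cycles, two cycles would last 2 × 29 = 58 days against 56 days for eight weeks. Section 11.4 fixes imaging every eight weeks from the first day of cycle 1 and does not let it move with cycle delays, so the response assessments do not follow this drift.

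**The case against.** The strongest reply is that the cell's only explicit day range, days 1 to 22, already covers the infusion. On that range there is no sunitinib-free TH-302 dose, and what remains is a six-day rest loosely called a week, or a cycle one day too long. This is correct, and it makes the day-22 overlap conditional. It does not remove the contradiction, because the parenthesis in the same cell says something else and the documents do not say which governs. The range may have been written to cover day 22, or it may be a slip.

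A reader might infer that the protocol schedules a prohibited TH-302 monotherapy infusion in every level -2 cycle. The documents do not support that, for three reasons:

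- The overlap arises only on the 21-day reading.
- The ban sits in the section on discontinuing treatment, between a sentence on continuing sunitinib after TH-302 is stopped and one on stopping TH-302 when sunitinib is stopped. A planned rest day inside a combination cycle is not plainly what it addresses.
- Section 6.3, as worded, lets either drug be given on its own on day 8 or 22 when the other is postponed. The ban is therefore not applied consistently at the level of a single day.

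Nor do the documents show that sites will in fact diverge. Sections 6.3.1 and 6.3.3 offer routes for discussing dose reductions or specific cases with the sponsor or the coordinating investigator. These could settle queries, but only if a site notices the problem and asks. The defensible statement is that sites could differ.

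Finally, the size is small: one dose per affected cycle, and the documents give no expected number of patients at level -2. That stands.

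**Conclusion.** The level -2 sunitinib entry contradicts itself by one day (22 against 21 days on; 29 against 28 days in all), and that day carries a TH-302 infusion. The result rests only on inclusive counting, which the table's other rows establish, and on the 28-day cycle.

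The weekly reading conflicts with the assumption in Section 6.1.1 that sunitinib is taken on TH-302 days. Its conflict with the monotherapy ban in Section 6.3.1 is possible but not established. Separately, Sections 6.3 and 6.3.1 are in tension with each other whatever Table 1 is taken to mean.

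This is an internal contradiction in a dosing instruction, not a weakness of the design. It should be corrected for the sake of clear dosing and consistent exposure data. It is confined to level -2 cycles and to the reporting of omissions and compliance in them. The sample size, error rates and definition of objective response are untouched.

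**What to change.** The sponsor should amend Table 1 so that the day range, the weekly description and the 28-day cycle agree. The entry should state whether day 22 is a sunitinib day. It should then be checked against the timing rule in Section 6.1.1, the single-drug postponement rule in Section 6.3 and the monotherapy ban in Section 6.3.1. Section 6.3.1 should say whether the ban covers a planned sunitinib rest day, and its wording should be reconciled with Section 6.3. Which schedule to adopt is a clinical decision for the sponsor, and none is suggested here.

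The SAP should state the number of prescribed sunitinib days per level -2 cycle that is used to count omissions and compliance in Table 11.

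The cost is one table cell, a clarifying sentence in Sections 6.3 and 6.3.1, and one line in the SAP, which can go into a single amendment. Correcting the cell alone would not resolve the tension between Sections 6.3 and 6.3.1. No recalculation of the design is needed.

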6.3.4. Dose Titration According to the Type and Severity of Toxicity

Table 2. Titration according to haematological toxicity

ABSOLUTE NEUTROPHIL COUNT (ANC) (/μl)	AND /OR	PLATELET COUNT (/μl)	DOSE LEVEL WHEN REINTRODUCING TH-302		SUNITINIB
			Day 8	Day 22	
≥ 1500	AND	≥ 100,000	Starting	Starting	Starting
1000-1499	AND	75,000-99,999	Delay	Delay	Starting
500-999	OR	50,000-74,999	Delay and reduce one level in following cycles	Delay and reduce one level in following cycles	Reduce one level
< 500	OR	< 50,000	Delay and reduce one level in following cycles	Delay and reduce one level in following cycles	Reduce one level

A phase II trial to assess the activity and safety of TH-302 in combination with sunitinib in patients

Table 3. Titration according to non-haematological toxicity

TH-302			
Toxicity grade	Toxicity	Discontinuation	Dose after recovery
Grade 2	Except for asthenia, alopecia, nausea, vomiting and diarrhoea	Until \leq grade 1 recovery	Starting
	Unacceptable skin abnormality	Until \leq grade 1 recovery	Reduce one level (-1)
Grade 3	Except for nausea and vomiting	Until \leq grade 1 recovery	Reduce one level (-1)
Grade 4	Potentially fatal (drug-related)	Permanent discontinuation	N/A
	Others such as non-life threatening asthenia or pulmonary embolism	Until \leq grade 1 recovery	Reduce two levels (-2)

Table 4. Titration according to non-haematological toxicity

Sunitinib			
Toxicity grade	Toxicity	Discontinuation	Dose after recovery
Creatinine > x2 upper limit of normal (ULN)	Irrespective of the cause	Until creatinine \leq x2 upper limit of normal (ULN)	Reduce one level (-1)
Grade 2	Except for asthenia, alopecia, nausea, vomiting and diarrhoea	Until \leq grade 1 recovery	Starting
Grade 3	Except for nausea and vomiting	Until \leq grade 1 recovery	Reduce one level (-1)
Grade 4	Potentially fatal (drug-related)	Permanent discontinuation	N/A
	Others such as non-life threatening asthenia or pulmonary embolism	Until \leq grade 1 recovery	Reduce one level (-1)

Table 5. Titration according to ECG QTc interval prolongation

	Presence of a reversible cause	Unidentified reversible cause
G2 QTc interval prolongation	
 - Treat the reversible cause. - ECG monitoring. * - If first event, continue TH-302 at the same dose if QTc < G2 (≤ 480 msec) - If relapse, G2 or QTc > 480 msec more than two cycles after correction of the possible causes, and with no other identifiable cause, the dose will be titrated after consulting a cardiologist and GETNE, in accordance with the available TH-302 safety data and the investigator's good medical practice. 	
 - ECG monitoring.* - If first event, continue TH-302 at the same dose. - If relapse or QTc > 480 msec more than two cycles after correction of the possible causes, and with no other identifiable cause, the dose will be titrated after consulting GETNE, in accordance with the available TH-302 safety data and the investigator's good medical practice.
G3 QTc interval prolongation	
 - Treat the reversible cause. - ECG monitoring. * - Discontinue treatment until QTc ≤ 500 msec. - Reintroduce TH-302 at the same dose - If G3 recurs, future dose titration will be performed after consulting a cardiologist and GETNE, in accordance with the available TH-302 safety data and the investigator's good medical practice. 	
 - ECG monitoring. * - Discontinue treatment until QTc ≤ 500 msec. - Reintroduce treatment with one-level dose reduction. - If G3 recurs, despite dose reduction, future dose titration will be performed after consulting a cardiologist and GETNE, in accordance with the available TH-302 safety data and the investigator's good medical practice.
G4 QTc interval prolongation	Permanent treatment discontinuation	Permanent treatment discontinuation

* In the event of a QTc interval prolongation and during treatment discontinuation, the frequency of performing control ECGs should be increased to once a week (the same day each week), together with electrolytes analysis, until the QTc interval ≤ 480 msec ($\leq G1$).
		

6.3.5. Medication Errors or Overdose

Medication errors may be due to a timing error or the drug dosage. These cases should be recorded as an adverse event (AE) or severe adverse event (SAE), as appropriate, in the CRF.

A phase II trial to assess the activity and safety of TH-302 in combination with sunitinib in patients

Should a medication error occur, GETNE must be notified immediately [REDACTED]

Examples of a medication error:

- Medication errors that involve patient exposure to the drug (dispensation/administration of expired medication, dispensation of commercial sunitinib or TH-302 or not allocated for this trial, etc.)
- Medication errors or practices not in accordance with the protocol and that may or may not involve the patient participating in the study (deviations from relevant temperatures, trial medication stock mismatches, etc.).

An SAE will be reported where a patient voluntarily or accidentally ingests more than 60 sunitinib tablets in a single cycle (for example, more than 4 tablets in more than 2 days within a cycle or more than 4 tablets in one day).

An AE will be reported in cases where a patient voluntarily or accidentally ingests 58 or 60 sunitinib tablets in a single cycle. The event will be recorded in the CRF.

Any TH-302 dosage error which leads to > 20% of the expected dose should be considered a TH-302 overdose.

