10.2.2 Adverse Events

An adverse event is defined as any unwanted or unintended symptom, sign, disease or experience (including a clinically significant laboratory result of any grade according to the common terminology criteria for adverse events [*CTCAE*] of the National Cancer Institute, version 4.0) that emerges or worsens during the course of the study, whether related or not to the study drug.

The assessment of adverse events will include type (symptoms from the medical history, physical examination findings or laboratory/ECG/radiological/other diagnostic procedure abnormalities), prevalence, severity/seriousness, time and their link.

Examples of adverse events are the following:

- Deterioration (excluding mild fluctuations) of the nature, intensity, frequency, or duration of a pre-existing condition.
- Development of an intercurrent illness during the study.
- Development of symptoms that may or may not be associated with the use of a concomitant medication or the study drug.
- Injury or accidents: if a medical condition is known to have caused the injury or accident, both the medical condition as well as the accident should be recorded as two independent medical events (e.g., in the event of a fall caused by dizziness, both the “fall” and the “dizziness” must be recorded separately).

The following situations will not be classified as adverse events:

A phase II trial to assess the activity and safety of TH-302 in combination with sunitinib in patients

- Medical or surgical procedures (e.g., surgery, endoscopy, tooth extraction, transfusion). However, the disease precipitating the procedure is an adverse event.
- Pre-existing conditions or diseases present or detected prior to the first administration of the study drug that do not deteriorate.
- Circumstances in which no unwanted medical events manifest (e.g., hospitalisation for elective surgery, hospitalisations for social circumstances and/or convenience).

The relationship between the adverse event and the study drug:

The reasonable possibility of a link between the adverse event and the study drug will be determined. In cases where the study site investigator is unable to make an objective judgement, the opinion of the clinical monitor should be sought. The following definitions will be used:

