10.2.3. Intensity Grading of Adverse Events

Adverse events and their severity will be assessed based on *National Cancer Institute Common Terminology Criteria for Adverse Events* (NCI-CTCAE, version 4.0). These criteria can be consulted at the following address:

http://evs.nci.nih.gov/ftp1/CTCAE/CTCAE_4.03_2010-06-14_QuickReference_8.5x11.pdf

10.2.4. Serious Adverse Events (SAEs):

A serious adverse event (SAE) or reaction is any harmful medical event that, regardless of the dose:

- Results in the death of the patient.
- Is life-threatening to the patient or potentially fatal (i.e., the patient is at immediate risk of death at the time of the event).
- Requires patient hospitalisation or the prolongation of existing hospitalisation.
- Results in permanent or significant disability or incapacity.
- Causes a defect, congenital malformation or results in cancer.

In addition, medical and scientific judgement should be used to decide whether other situations should be considered as a serious adverse event, although they do not meet the above criteria, such as those that endanger the patient's life or require intervention to prevent any of the above outcomes.

It must not be confused with the term "severe", which indicates the intensity of the adverse event.

Recording and Reporting of Serious Adverse Events (SAEs):

Information on SAEs, whether related to the treatment or not, will be collected and recorded on the SAE form of the corresponding case report form. SAEs, as defined above, must be recorded from the date the informed consent form was signed, and the pharmacovigilance contact person must be notified immediately, within 24 hours of awareness by the study site, by fax to

Marketing Farmacéutico & Investigación Clínica

The initial report must state the site name and number, the name of the investigator, the patient ID number and initials, patient demographics, study drug administration data and everything known about the serious adverse event, including date of onset, intensity, treatment and relationship to the study drug. If the patient dies, the report should include the cause of death and its potential relationship to the study drug, in addition to the autopsy findings (if available).

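### Section 6.3.5 makes sunitinib counts and dosing errors reportable as AEs or SAEs without a clinical event, against the definitions in 10.2.2 and 10.2.4

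*Protocol*

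**What the plan says.** Protocol 6.3.5 opens with "Medication errors may be due to a timing error or the drug dosage" and continues: "These cases should be recorded as an adverse event (AE) or severe adverse event (SAE), as appropriate, in the CRF". It then requires immediate notice to the sponsor. After that it gives examples of a medication error, among them practices "that may or may not involve the patient participating in the study (deviations from relevant temperatures, trial medication stock mismatches, etc".

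Two rules based on counts follow. "An SAE will be reported where a patient voluntarily or accidentally ingests more than 60 sunitinib tablets in a single cycle"; the illustrations in brackets include more than 4 tablets on a single day. Then: "An AE will be reported in cases where a patient voluntarily or accidentally ingests 58 or 60 sunitinib tablets in a single cycle". Neither rule mentions a symptom, sign or other clinical consequence.

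Protocol 10.2.2 defines an AE as an unwanted or unintended symptom, sign, disease or experience. Among the situations that are not AEs it lists "Circumstances in which no unwanted medical events manifest". Protocol 10.2.4 defines an SAE as a harmful medical event with one of several listed outcomes, and leaves room for medical judgement on other situations. It says of the term serious adverse event: "It must not be confused with the term" severe, which describes intensity.

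SAP 1.5.5.1 and 2.8 present AEs and SAEs descriptively, with AEs summarised by maximum CTCAE grade. Neither section says what happens to a record that consists only of a medication error.

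**The concern.** A patient who takes too many capsules in a cycle and feels nothing has an AE or SAE under 6.3.5. The same patient has neither under a plain reading of 10.2.2 and 10.2.4. The same holds for a harmless timing error: 6.1.1 asks for sunitinib at the same hour each day and two hours away from the TH-302 infusion, so lapses of this kind can be expected.

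Safety is part of the trial's main purpose (Protocol 1.12), and AEs and SAEs are what the safety analysis reports. Ten sites must choose between two rules. Their counts may then not mean the same thing, and an SAE figure could mix harm with dosing irregularities that caused none. Writing SAE out as severe adverse event in 6.3.5 adds to the risk, because it invites the confusion that 10.2.4 warns against.

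**Working it through.** The plan gives no figure on this point, so there is none to reproduce. The check has three parts.

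**1. The rules side by side, for an error with no clinical consequence**

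| Situation | 6.3.5 | 10.2.2 / 10.2.4 |
|---|---|---|
| Timing or dosage error | AE or SAE, as appropriate | Not an AE if no unwanted medical event occurs |
| 58 or 60 tablets in a cycle | AE | Not an AE if no unwanted medical event occurs |
| More than 60 tablets in a cycle | SAE | Not an SAE without a harmful medical event |
| Stock mismatch or temperature deviation | Named as an example; recording category unclear | Not an AE |

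The second and third rows are the clearest conflict, because the count rules carry no qualifier.

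**2. The count rule against the planned dose**

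Inputs: 2 capsules a day (6.1.1) and a 28-day cycle. I assume that a tablet in 6.3.5 means one capsule.

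- Planned count: 2 × 28 = 56.
- The SAE rule starts at 61, which is 61 − 56 = 5 extra capsules in four weeks (5/56 = 8.9%).
- The AE rule names 58 and 60 only. Totals of 57 and 59 fall under neither rule.
- One-day example, other days as planned: 27 × 2 = 54. Five tablets on the odd day give 54 + 5 = 59, six give 60, and seven give 61. So the example, offered as an SAE of more than 60, can total 59, which has no category, or 60, which the next sentence makes an AE.
- At dose level −2 (21 or 22 sunitinib days, depending on how Table 1 is read) the planned count is 42 to 44. The same SAE threshold is then 61 − 44 = 17 to 61 − 42 = 19 extra capsules.

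**3. Possible effect on a per-patient rate**

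Increase = m(1 − q)/N. N = 43 is the planned enrolment (Protocol 5.4, SAP 1.5.4). The number of patients with a harmless recorded error is m, and q is the share of them who already count through a true event. The documents give neither m nor q, so both are assumptions.

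| m | q = 0 | q = 0.5 | q = 1 |
|---|---|---|---|
| 1 | 2.3 points | 1.2 | 0 |
| 2 | 4.7 | 2.3 | 0 |
| 4 | 9.3 | 4.7 | 0 |

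For example, with m = 2 and q = 0.5: 2 × 0.5/43 = 2.3 points.

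**The case against.** The best defence is that 6.3.5 is a deliberately cautious reporting rule. The recording sentence is qualified by the words as appropriate. The AE definition in 10.2.2 includes any unintended experience, and its exclusion is illustrated by elective and social hospitalisations, not by dosing errors. Section 10.2.4 lets judgement make other situations serious. A sponsor may well want every overdose reported quickly, with or without symptoms. The safety analysis is descriptive, and no decision hangs on an AE or SAE rate.

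Much of this stands for a true overdose, and it is why the reporting trigger should not be removed. It does not settle the conflict. As appropriate can be read as a choice between AE and SAE only. The judgement clause in 10.2.4 is illustrated by danger to life or a need to intervene, whereas a tablet count involves no judgement. Nothing in the SAP separates records made for reporting from events that were harm.

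A reader might go further and infer that 6.3.5 orders stock mismatches and temperature deviations to be entered as AEs, and that the safety rates are thereby inflated. The documents do not support either step. The recording sentence follows directly on timing and dosage errors. The storage and stock examples come later, after the separate instruction to notify the sponsor, so how to record them is unclear rather than ordered. An event without a patient has no eCRF, since 13.2 provides one per enrolled patient, and it adds nothing to a percentage of patients. Nor is inflation from patient-level errors shown. For the any-AE rate it may well be close to nil: section 3.4 lists eight AE types seen in 20% or more of patients on weekly TH-302, so few patients may have an error as their only record. A harmless error also has no evident CTCAE grade or row in SAP Table 34. The any-SAE rate is the more exposed of the two.

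**Conclusion.** The concern holds as an internal inconsistency. Section 6.3.5 makes patient-level errors and sunitinib counts reportable as AEs or SAEs without a clinical event. Sections 10.2.2 and 10.2.4 require one, and the term severe in 6.3.5 conflicts with serious in 10.2.4. The count thresholds also do not agree with their own example and leave 57 and 59 without a category.

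The consequence is that symptom-free errors can be counted at some sites and not at others. The size is 2.3 percentage points for each patient counted only for that reason, on 43 patients, and 0 for a patient with a true event of the same class. How many such patients there would be cannot be found from the documents; the table shows assumed values only. No conclusion is drawn that the rates will be inflated, and none on which threshold is right.

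**What to change.** In Protocol 6.3.5:

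- Reconcile the section with 10.2.2 and 10.2.4 by stating whether a medication error or a capsule count without a clinical event is an AE or SAE.
- Reconcile the count thresholds with each other and with the one-day example. Which of them is right is for the sponsor to settle.
- Change severe to serious where SAE is written out.
- State that storage and stock deviations are recorded as protocol deviations.
- Keep the immediate notice to the sponsor and the expedited reporting of overdose. An SAE goes to pharmacovigilance within 24 hours under 10.2.4, which is a separate channel from the sponsor notice in 6.3.5. A redefinition that simply dropped the count-based SAE would therefore lose a safety report.

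In SAP 1.5.5.1 and 2.8, state that records consisting only of a medication error, with no clinical event, are shown in a separate listing and left out of the AE and SAE rates. Reporting and tabulation are then handled apart: an overdose is still reported quickly, and the rates describe harm.

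The cost is wording in both documents, one CRF flag and one extra listing. SAE totals in the pharmacovigilance records and in the SAP tables may differ by the flagged records, and the listing accounts for that difference.
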